### **3. SCHEDULE OF ASSESSMENTS**

The study schedule of assessments can be found in Table 1.A.

## Schedule of Assessments

	Screening	Baseline		Double Blind Treatment					Optional Visit (Suture Removal)
	Visit 1	Visit 2	Visit 3	Visit 4	Visit 5	Call	Visit 6	Visit 7	
Week		0	0	1	2	4	4	4	6
Treatment Day	-30 to 0	1	2	8	15	27	28	29	43
Treatment Window(days)	N/A	N/A		± 3	± 3	-3	-3	-3	± 3
Informed consent 	X								X 
Inclusion/exclusion criteria	X	X							
Physical exam 	X								X
Demographics & medical history	X								
Alopecia Areata History	X								
Vital signs 	X	X	X	X	X		X	X	X
Clinical laboratory sampling  : CBC, Chemistry with lipids, Virology, Serum Pregnancy, Urinalysis	X 	X			X			X	
Urine pregnancy test (WOCBP) 		X					X		
ECG	X	X			X			X	
SALT Score (prior to ALODEX) 		X						X	
ALODEX Score (after SALT) 		X						X	
Clinician Eyebrow Assessment									X 
Subject Eyebrow Assessment									X 
Subject Global Impression of Treatment Satisfaction (SGIS)									
Photography 		X						X	
Subject randomization		X							
Subject instructions 		X	X	X	X	X	X	X 	
Biopsy for PK 			X						X
Biopsy for PD 			X						X
Blood sample for PK 			X	X			X	X	
Blood for immunologic studies 			X					X	
Dispense, collect, weigh study medication bottles 			X	X	X	X	X	X 	
In office study medication application 			X				X		
Suture removal, if applicable 					X				X
Telephone Call 						X			
Concomitant therapies			X		X	X	X	X	X
Adverse events			X	X	X	X	X	X	X
	Open-Label Treatment								Post-Treatment 

	Visit 8	Visit 9	Visit 10	Visit 11	Visit 12	Call	Visit 13	Optional Visit (Suture Removal)	Visit 14	Visit 15	Visit 16
Week	8	12	16	20	24	28	28	30	40	52	56
Treatment Day	57 (OLE 28)	85 (OLE 56)	113 (OLE 84)	141 (OLE 112)	169 (OLE 140)	196 (OLE 167)	197 (OLE 168)	211 (OLE 182)	281 (OLE 252)	365 (OLE 336)	59/ 393 (OLE 364)
Treatment Window(days)	± 3	± 3	± 3	± 3	± 3	± 3	± 3	± 3	± 7	+7	± 3/± 7
Informed consent 											
Inclusion/exclusion criteria											
Physical exam 											X
Demographics & medical history											
Alopecia Areata History											
Vital signs 	X	X	X	X	X		X	X	X	X	X
Clinical laboratory sampling  :		X					X		X	X	X
CBC, Chemistry with lipids, Virology, Serum Pregnancy, Urinalysis											
Urine pregnancy test (WOCBP) 	X	X	X	X	X		X		X	X	X
ECG		X					X				X
SALT Score (prior to ALODEX) 	X	X	X	X	X		X		X	X	X
ALODEX Score (after SALT) 	X	X	X	X	X		X		X	X	X
Clinician Eyebrow Assessment	X	X	X	X	X		X		X	X	X
Subject Eyebrow Assessment	X	X	X	X	X		X		X	X	X
Subject Global Impression of Treatment Satisfaction (SGIS)	X	X	X	X	X		X		X	X	
Photography 	X	X	X	X	X		X		X	X	
Subject randomization											
Subject instructions 	X	X	X	X	X		X		X	X	
Biopsy for PD 							X				
Blood for immunologic studies 							X				

	Open-Label Treatment										Post-Treatment 
	Visit 8	Visit 9	Visit 10	Visit 11	Visit 12	Call	Visit 13	Optional Visit (Suture Removal)	Visit 14	Visit 15	Visit 16
Week	8	12	16	20	24	28	28	30	40	52	56
Treatment Day	57 (OLE 28)	85 (OLE 56)	113 (OLE 84)	141 (OLE 112)	169 (OLE 140)	196 (OLE 167)	197 (OLE 168)	211 (OLE 182)	281 (OLE 252)	365 (OLE 336)	59/ 393 (OLE 364)
Treatment Window(days)	± 3	± 3	± 3	± 3	± 3	± 3	± 3	± 3	± 7	+7	± 3/± 7
Dispense, collect, weigh study medication bottles 		X	X	X	X	X	X		X	X	
In office study medication application 		X									
Suture removal, if applicable 								X		X	
Telephone Call 						X					
Concomitant therapies		X	X	X	X	X	X	X	X	X	X
Adverse events		X	X	X	X	X	X	X	X	X	X
 A written signed ICF must be obtained from each subject prior to performing any study related procedure (i.e., prior to performing vital signs, standardized photography, biopsies, clinical laboratory sampling, or UPT).											
 A physical exam includes: General appearance, examination of head, eyes, ears, nose and throat, respiratory, cardiovascular, abdominal, neurological, musculoskeletal, lymphatic and skin assessment.											
 Vital signs include oral or ear temperature, blood pressure, heart rate, respiration rate (height and weight at Baseline only).											
 Clinical laboratory sampling includes: CBC, Chemistry with lipids, Urinalysis, at each visit and At Screening only: Quantiferon Gold, TIBC, Serum iron, Serum Ferritin, Serum pregnancy, T3, T4, and TSH.											
 UPT must be performed prior to randomization at Visit 2 and prior to study medication application at Day 28 (Visit 6) and at each OLE visit. UPT must be negative for the subject to continue in the study. WOCBP must have a negative serum pregnancy test at screening and a negative UPT at baseline prior to randomization.											
 SALT is performed prior to ALODEX score using device provided.											
 ALODEX is performed after SALT score using device provided.											
 Photography should be performed on Day 1 (prior to application of study medication application) and on Day 29 & Day 197 prior to the scalp biopsy.											
 Subjects must be instructed to apply the study medication according to the instructions in Appendix 1. Subjects will apply the first dose of study medication on the morning of Day 1 (Visit 2) and the last application of study medication on the morning of Day 28 (Visit 6), under the instruction and supervision of the study staff. Study medication at these visits should be applied in the morning to allow the 8-hour post dose assessments to occur at a reasonable time. On Day 1 (Visit 2) and Day 29 (Visit 7) subjects will only apply study medication once-a-day in the office.											
 PK: A 4mm punch biopsy must be obtained on Day 2 (Visit 3) and Day 29 (Visit 7) 24 hours (± 30 minutes) after study medication application on Day 1 (Visit 2) and Day 28 (Visit 6).											
 PD: A 4mm punch biopsy must be obtained on Day 1 (Visit 2) before application of first dose of study medication and Day 29 (Visit 7) 24 hours (± 30 minutes) after study medication application. Subjects that choose to continue in to open-label extension treatment will also have a 4mm punch biopsy collected on Day 197 (Visit 13).											

	Open-Label Treatment										Post-Treatment  Visit 16
	Visit 8	Visit 9	Visit 10	Visit 11	Visit 12	Call	Visit 13	Optional Visit (Suture Removal)	Visit 14	Visit 15	
Week	8	12	16	20	24	28	28	30	40	52	56
Treatment Day	57 (OLE 28)	85 (OLE 56)	113 (OLE 84)	141 (OLE 112)	169 (OLE 140)	196 (OLE 167)	197 (OLE 168)	211 (OLE 182)	281 (OLE 252)	365 (OLE 336)	59/ 393 (OLE 364)
Treatment Window(days)	± 3	± 3	± 3	± 3	± 3	± 3	± 3	± 3	± 7	+7	± 3/± 7
 PK: The first 6 subjects enrolled in the study will have the blood PK testing performed. Blood for PK sampling will be obtained on Day 1 (Visit 2) and Day 28 (Visit 6), just prior to study medication application (predose), and 1, 2, 4, 8 hours post dose and on Day 2 (Visit 3) and Day 29 (Visit 7), 24 hours after study medication application (on Day 1 (Visit 2) and Day 28 (Visit 6). See Section 9.3.2 for PK sample draw time windows.											
 Blood for immunology will be obtained prior to administration of study medication on Day 1 (Visit 2) and on Day 29 (Visit 7) 24 hours (± 30 min) after study medication application on Day 28 (Visit 6). Subjects that choose to continue in to open-label extension treatment will also have blood for immunology collected on Day 197 (Visit 13).											
 On Day 1 (Visit 2) and Day 28 (Visit 6) the study medication bottle should be weighed and then dispensed to the subject for the initial application under the supervision of study staff in the office. After the initial application on Day 1, the study medication bottle should be collected, weighed and dispensed to the subject after the 24-hour post-dose blood draw on Day 2 (Visit 3). For Visits 3 -6, each study medication bottle (with the cap) must be weighed before dispensing to the subject and at the time of return using the scale provided by Aclaris. On Day 28 (Visit 6), the study medication bottle should be weighed after subject applies the study medication in the office and not redispensed.											
 The investigator or designee will remove the sutures approximately 14 days after scalp biopsy, unless an absorbable suture is used.											
 On Day 27 or the day prior to Day 28 (Visit 6), the study staff will call the subject to remind them not to apply study medication on the morning of Day 28 (Visit 6) and to bring both used and unused study medication bottles to the visit. Study medication will be applied in the office under the supervision of the study staff. On Day 196 or the day prior to Week 28 (Visit 13) the study staff will call the subject to remind them not to apply study medication in that evening and on the morning of Week 28 (Visit 13), and to bring both used and unused study medication bottles to the visit. The scalp biopsy at Week 38 (Visit 13) should be performed 24 hours (±30 minutes) post the last study medication application.											
 On Day 29 (Visit 7) subject may be given the option to move into open-label extension treatment. 
 
• If the subject declines the open-label extension, she/he should be seen for the Visit 16 (Post-treatment) assessments 30 days following the date of Day 29 (Visit 7).
 
• If the subject chooses to continue in to the open-label extension, she/he must sign an ICF prior to being dispensed open-label drug and receiving continued study medication application instructions.
 
• If the subject enrolls in open-label treatment after Day 29 (Visit 7), an unscheduled visit will be conducted in order to obtain consent, review drug application instructions, and dispense drug. This will be considered the official date that the subject initiated open-label extension treatment and the scheduling of subsequent visits 8-16 should be based off of this date as referenced by (OLE xxx) in the treatment day schedule header above.
 
											
 Subjects who are eligible and consent to enter the open-label extension will have a baseline CEA and SEA completed at Visit 7 or the unscheduled Visit.											

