7.5. Duration of the Study

The anticipated time for study enrollment is 3 to 6 months. The duration of the screening period is up to 30 days. The expected double-blind treatment period for each subject is 29 days (maximum of 28 days of study medication application). The post-treatment follow-up period is up to 33 days (30 + 3-day window). The maximum total study duration for the double-blind period from the subject's first visit (Visit 1) through the subject's last visit (Visit 8) is 92 days. On Day 1 (Visit 2) and Day 28 (Visit 6), subjects are required to be confined at the investigational center until all study procedures are completed. The confinement period may last approximately 10 hours. The duration of the total study participation from Baseline (Visit 2) to the open-label post-treatment follow up visit, Week 56 (Visit 16) is anticipated to be a maximum of 400 days. The duration of the open-label extension (OLE) should be based on the date of the visit that the subject initiated OLE treatment rather than the days from Baseline (Visit 2). For subjects who entered the open-label extension and had a gap between Visit 7 and entry into the open-label extension due to an administrative delay total study participation may be longer than 400 days.

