9.1. Efficacy Assessments

9.1.1. Severity Alopecia Tool (SALT) Score

The SALT score is a measurement of the amount of scalp without any hair. The Investigator will assess the SALT score using an iPAD provided by Aclaris at Baseline (Visit 2), Day 29 (Visit 7), and as detailed in Section 7.3 for the subjects who continue in the open-label extension. Equipment, supplies, training and a detailed Reference Guide will be provided to the investigational site prior to the initiation of subject enrollment.

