## **4.3 Pharmacodynamic Endpoints**

The baseline scores for SALT and ALODEX will be the last non-missing value collected  $\leq$  the date of the first application of double-blind study medication. This baseline will be used also for calculating changes during open-label for these variables. For the eyebrow assessments (CEA and SEA), the value collected at V7 will be used as the baseline for calculating changes during subsequent visits.

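### For late entrants to the open-label extension, SALT and ALODEX change includes the off-drug gap and cannot be split from change on drug, and the eyebrow baseline rule does not match the schedule

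*SAP*

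**What the plan says.** **The gap.** Protocol 7.5 provides for subjects who "had a gap between Visit 7 and entry into the open-label extension due to an administrative delay". The protocol's amendment history refers to an administrative letter of 03AUG2018 on the same subjects. Neither document gives a gap length or a count.

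**The entry visit.** For late entrants, footnote 17 of the Schedule of Assessments (the same in protocol and SAP) says "an unscheduled visit will be conducted in order to obtain consent, review drug application instructions, and dispense drug". That date becomes the official start of open-label treatment, and the "scheduling of subsequent visits 8-16 should be based off of this date". Footnote 18 adds that subjects entering the extension "will have a baseline CEA and SEA completed at Visit 7 or the unscheduled Visit". SALT, ALODEX and photography are not listed for this visit.

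**Scalp scores.** Protocol 9.1.1 has SALT assessed "at Baseline (Visit 2), Day 29 (Visit 7), and as detailed in Section 7.3 for the subjects who continue in the open-label extension"; 9.1.2 gives ALODEX the same times. In Section 7.3 the next scores are at Visit 8, OLE Day 28.

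**Baselines.** SAP 4.3 says "The baseline scores for SALT and ALODEX will be the last non-missing value collected" on or before the date of first double-blind application, and then "This baseline will be used also for calculating changes during open-label for these variables". For CEA and SEA, "the value collected at V7 will be used as the baseline for calculating changes during subsequent visits". SAP 4.3.1 builds mean change and the ≥25%, ≥50% and ≥75% regrowth proportions on the scalp baseline. Protocol 12.5.4 also measures scalp change from Visit 2, but measures eyebrow change from entry into the extension.

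**The concern.** The Week 28, 40 and 52 SALT and ALODEX results are the trial's main efficacy evidence, and they come from an uncontrolled period. For a late entrant, the tabulated change at those visits joins three stretches: 28 double-blind days (on vehicle for about 4 of the 12 subjects), the off-drug gap, and the open-label days. Visit 7 separates the first stretch from the rest. Nothing scheduled separates the second from the third. The last scalp score before open-label drug is Visit 7, or a Day 59 post-treatment visit if one was held and scored. A score not taken at entry cannot be recovered later.

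The eyebrow endpoints have a different weakness. The schedule lets the baseline be taken at either of two visits, and the analysis recognises only one of them.

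**Working it through.** **1. Schedule check.** Section 7.3 gives study day / OLE day as 57/28 (Visit 8), 197/168 (Visit 13), 281/252 (Visit 14) and 365/336 (Visit 15). The difference is 29 each time, and it is also 29 at Visit 16 (393/364). The stated maximum reproduces: 393 + 7 = 400 days. There is no power calculation to check, because SAP 4.7 bases N = 12 on feasibility.

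**2. What the change covers.** Let g be the gap in days (an assumption, since the documents give none).

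Days from Visit 2 to an open-label visit = 28 + g + OLE day; gap share = g ÷ that total.

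| g | Visit 8 | Visit 13 (Week 28) | Visit 14 (Week 40) | Visit 15 (Week 52) |
|---|---|---|---|---|
| 0 | 0/56 = 0% | 0/196 = 0% | 0/280 = 0% | 0/364 = 0% |
| 28 | 28/84 = 33.3% | 28/224 = 12.5% | 28/308 = 9.1% | 28/392 = 7.1% |
| 84 | 84/140 = 60.0% | 84/280 = 30.0% | 84/364 = 23.1% | 84/448 = 18.8% |
| 168 | 168/224 = 75.0% | 168/364 = 46.2% | 168/448 = 37.5% | 168/532 = 31.6% |

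The top of this range is an extreme. Protocol Version 1.0 is dated 26JUL2017, and Amendment 1, which created the extension, is dated 06FEB2018. Dosing on the protocol's own date would put Visit 7 on 23AUG2017, 167 days before Amendment 1. Site approval time would add to any gap. No actual Visit 7 date is given.

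**3. Effect on a regrowth proportion (hypothetical scores).** SAP 4.3.1: relative regrowth = −(score − baseline) ÷ baseline.

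- SALT 100 at Visits 2 and 7, 90 at entry, 75 at Visit 13. From Visit 2: 25/100 = 25.0%. From entry: 15/90 = 16.7%. The subject meets the ≥25% cut only on the SAP basis.
- Entry SALT at the limit of the >95% inclusion criterion, same course otherwise. From entry: (95 − 75)/95 = 21.1%, so the difference from 25.0% is at most 3.9 points.
- Opposite direction: SALT 96 at Visits 2 and 7, 100 at entry, 73 at Visit 13. From Visit 2: 23/96 = 24.0%. From entry: 27/100 = 27.0%. Here hair loss in the gap hides a responder.

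One subject crossing a cut moves a proportion by 1/12 = 8.3 points, or 1/8 = 12.5 points if only 8 are analysed.

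**4. Which rule does what.** Suppose an entry SALT had been taken. SAP 4.3 would still use the score before double-blind treatment, so every planned change from baseline and regrowth proportion at Visits 8 onward would be unchanged. The baseline rule puts the gap into those summaries. The missing score prevents anyone from taking it out.

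**5. Eyebrow baseline for a late entrant.**

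| CEA/SEA scored at | Footnote 18 | Result under SAP 4.3 |
|---|---|---|
| Visit 7 only | Allowed | Visit 7 used; gap included in the change |
| Unscheduled visit only | Allowed | No Visit 7 value; no change can be calculated, as SAP 4 imputes only dates |
| Both | Not excluded | Visit 7 used; entry value ignored |

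The second row is plausible. The amendment history shows that the eyebrow assessments came in with Amendment 1, so a subject past Visit 7 by then may have no Visit 7 value. SAP 4.3.2 treats Visit 7 and extension entry as the same moment, which is untrue for these subjects.

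**The case against.** The strongest case against is that little is lost.

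- The protocol calls spontaneous regrowth in AT/AU rare, puts early vellus regrowth at 3 to 6 months at least, and expects none in the 28 double-blind days.
- Entrants must still satisfy the entry criteria. If that is applied at a late entry visit, SALT loss is above 95% there and regrowth in the gap is bounded as in the second example.
- Efficacy is secondary, descriptive and unpowered. Even a perfect entry score would not supply a control arm.
- Visit 2 is the prespecified scalp baseline, and exposure is already summarised by period.
- The Data Handling and Programming Specifications, which are not available here, may cover part of this.

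Most of this stands, and it limits the size of the point. Two parts do not settle it. The eligibility check is tied to Day 29, and the schedule shows no criteria review or SALT at the unscheduled visit, so the bound cannot be verified there (and it does not apply to ALODEX). A data-handling document cannot supply a score that was never scheduled.

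A reader might infer three stronger things that the documents do not support:

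- **That the missing score causes gap change to be counted.** Step 4 shows that the SAP 4.3 baseline does this.
- **That late entrants receive a fresh eyebrow baseline while the scalp was overlooked.** The schedule only permits one, and the analysis uses Visit 7. Eyebrows also have no earlier score, whereas the scalp has Visits 2 and 7.
- **That the results overstate the drug's effect.** Loss in the gap would work against it, and the planned tables describe cumulative change from Visit 2 without a test.

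**Conclusion.** The point holds as a limit on interpretation and an inexpensive improvement. It is not evidence of a biased result. For subjects with a gap, the open-label SALT and ALODEX summaries include off-drug change in an unknown direction, and the planned assessments cannot separate it from change on open-label drug. The time shares in step 2 rest on assumed gaps and say nothing about effect. The real effect is probably small given the protocol's own expectations, but with about 12 subjects a single crossing of a regrowth cut is visible.

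The eyebrow mismatch is a plain inconsistency between footnote 18 and SAP 4.3. It leaves a subject first scored at the unscheduled visit without a usable baseline. How many subjects either problem affects cannot be told from the documents.

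**What to change.** 1. **Schedule, footnotes 17 and 18 (protocol and SAP).** For late entrants, add SALT, then ALODEX, then photography at the unscheduled visit, before the first open-label application.
2. **SAP 4.3 and 4.3.1.** Keep Visit 2 as the main scalp baseline. Add a supportive summary or listing of change from the last SALT and ALODEX score on or before the first open-label application, using Visit 7 where no entry score exists. Show gap days per subject, and give the Week 28, 40 and 52 regrowth proportions with and without gap subjects.
3. **SAP 4.3 and 4.3.2.** Define the CEA and SEA baseline as the last value on or before the first open-label application. This agrees with footnote 18 and with the change from extension entry in Protocol 12.5.4.

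The cost is one extra tablet-based scalp assessment and a set of photographs at a visit already held, for late entrants only, plus one table or listing. For subjects already in the extension only the SAP changes (items 2 and 3) can apply. For them the split between gap and open-label change on the scalp stays unknown, and the report should say so.

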## 4. STATISTICAL METHODS

In general summaries will be presented according to double-blind treatment group and additionally for the subset of patients entering open-label. Other than baseline data (ie data collected prior to the first application of double-blind medication), the data summarized corresponds to the period of collection (ie during double-blind or during open-label). For those entering open-label, the open label period begins at the application of open-label medication. Additional details are provided in the data handling and programming specifications document. No imputation of missing data was performed other than completely or partially missing dates as described in the Data Handling and Programming Specifications document.

All Data listings are sorted by double-blind treatment group and patient ID.

### 4.1 Study Populations, Disposition, Baseline Characteristics, Medical History Concomitant Medications, Exposure and Protocol Violations

#### 4.1.1 Analysis Populations

The efficacy and safety populations will be defined as follows:

- As-Treated population (AS): This population includes all patients with at least one application of study treatment. This population will be used for pharmacodynamics and safety analyses. All analyses using this population will be based on the treatment actually received.
- Blood Pharmacokinetic (PK1) population: This population includes patients participating in the PK assessment who had evaluable blood plasma measurements with no significant protocol deviations that may impact the data.
- Scalp Pharmacokinetic (PK2) population: This population includes patients participating in the PK assessment who had evaluable scalp biopsy measurements with no significant protocol deviations that may impact the data.
- Pharmacodynamic (PD) population: This population includes all randomized patients who had at least 1 evaluable pharmacodynamic measurement.

#### 4.1.2 Patient Disposition

The number of patients in each population is presented together with the study completion status and the reasons for discontinuation. Patients entering open-label are considered to have completed the study with regard to double-blind medication.

#### **4.1.3 Demographic and Baseline Characteristics**

Demographic and baseline characteristics are presented in the data listings. Descriptive summary statistics (n, mean, standard deviation, median, minimum, and maximum) and/or frequency distributions, as appropriate, are generated for the AS population.

